7.2.1. Summaries of Numeric Laboratory Results

Descriptive statistics will be provided by treatment group for each laboratory test specified in the study protocol within hematology and chemistry panels including creatinine clearance, and also laboratory tests from lipids panel (under fasting status) including total cholesterol, LDL, HDL, triglycerides, non-HDL cholesterol (total cholesterol minus HDL cholesterol), LDL/HDL ratio, and total immunoglobulin (Ig), IgA, IgM, and IgG, as follows:

- Baseline values
- Values at each postbaseline time point
- Change from baseline at each postbaseline time point

A baseline laboratory value will be defined as the last measurement obtained on or prior to the date/time of first dose of study drug. Change from baseline to a postbaseline visit will be defined as the visit value minus the baseline value. The mean, median, Q1, Q3, minimum, and maximum values will be displayed to the reported number of digits; SD values will be displayed to the reported number of digits plus 1.

Median (Q1, Q3) of the observed change from baseline values for aspartate aminotransferase (AST), alanine aminotransferase (ALT), total bilirubin, alkaline phosphatase, serum creatine, creatinine clearance, creatine phosphokinase, white blood cell count, absolute neutrophils,

absolute lymphocytes, hemoglobin, platelets, total cholesterol, LDL, HDL, total Ig, IgG, IgA, and IgM, will be plotted using a line plot by treatment group and time point.

In the case of multiple values in an analysis window, data will be selected for analysis as described in Section 3.8.3.

7.2.2. Graded Laboratory Values

The CTCAE Version 4.03 will be used to assign toxicity grades (0 to 4) to laboratory results for analysis. Grade 0 includes all values that do not meet the criteria for an abnormality of at least Grade 1. For laboratory tests with criteria for both increased and decreased levels, analyses for each direction (ie, increased, decreased) will be presented separately.

7.2.2.1. Treatment-Emergent Laboratory Abnormalities

Treatment-emergent laboratory abnormalities are defined as values that increase at least 1 toxicity grade from baseline at any postbaseline time point, up to and including the date of last dose of study drug plus 30 days for subjects who permanently discontinued study drug, or the last available date in the database snapshot for subjects who were still on treatment at the time of an interim analysis. If the relevant baseline laboratory value is missing, any abnormality of at least Grade 1 observed within the time frame specified above will be considered treatment emergent.

7.2.2.2. Treatment-Emergent Marked Laboratory Abnormalities

Treatment-emergent marked laboratory abnormalities are defined as values that increase from baseline by at least 3 toxicity grades at any postbaseline time point, up to and including the date of the last dose of study drug plus 30 days for subjects who permanently discontinued study drug or the last available date in the database snapshot for subjects who were still on treatment at the time of an interim analysis. If the relevant baseline laboratory value is missing, any Grade 3 or 4 values observed within the timeframe specified above will be considered treatment-emergent marked abnormalities.

7.2.2.3. Summaries of Laboratory Abnormalities

The following summaries (number and percentage of subjects) for treatment-emergent laboratory abnormalities will be provided by lab test and treatment group; subjects will be categorized according to the most severe postbaseline abnormality grade for a given lab test:

- Graded laboratory abnormalities
- Grade 3 or 4 laboratory abnormalities
- Marked laboratory abnormalities

For all summaries of laboratory abnormalities, the denominator is the number of subjects with nonmissing postbaseline values up to 30 days after last dosing date.

A by-subject listing of treatment-emergent Grade 3 or 4 laboratory abnormalities will be provided by subject ID number and time point in chronological order. This listing will include all test results that were collected throughout the study for the lab test of interest, with all applicable severity grades displayed.

7.2.3. Liver-Related Laboratory Evaluations

Liver-related abnormalities after initial study drug dosing will be examined and summarized using the number and percentage of subjects who were reported to have the following laboratory test values for postbaseline measurements:

- Aspartate aminotransferase (AST): (a) > 3 times of the upper limit of normal (ULN) reference range; (b) $> 5 \times \text{ULN}$; (c) $> 10 \times \text{ULN}$; (d) $> 20 \times \text{ULN}$
- Alanine aminotransferase (ALT): (a) $> 3 \times \text{ULN}$; (b) $> 5 \times \text{ULN}$; (c) $> 10 \times \text{ULN}$; (d) $> 20 \times \text{ULN}$
- AST or ALT $> 3 \times \text{ULN}$ and total bilirubin $> 2 \times \text{ULN}$

The summary will include data from all postbaseline visits up to 30 days after the last dose of study drug. For individual laboratory tests, subjects will be counted once based on the most severe postbaseline values. For both the composite endpoint of AST or ALT and total bilirubin, subjects will be counted once when the criteria are met at the same postbaseline visit date. The denominator is the number of subjects in the Safety Analysis Set who have nonmissing postbaseline values of all relevant tests at the same postbaseline visit date. A listing of subjects who met at least 1 of the above criteria will be provided.

7.3. Body Weight and Vital Signs

Descriptive statistics will be provided by treatment group for body weight, BMI and vital signs (resting blood pressure [systolic blood pressure and diastolic blood pressure], respiratory rate, pulse and temperate) as follows:

- Baseline value
- Values at each postbaseline time point
- Change from baseline at each postbaseline time point

A baseline value will be defined as the last available value collected on or prior to the date/time of first dose of study drug. Change from baseline to a postbaseline visit will be defined as the postbaseline value minus the baseline value. Body weight and vital signs measured at unscheduled visits will be included for the baseline value selection.

In the case of multiple values in an analysis window, data will be selected for analysis as described in Section 3.8.3. No formal statistical testing is planned.

A by-subject listing of vital signs will be provided by subject ID number and time point in chronological order. Body weight, height, and BMI will be included in the vital signs listing, if space permits. If not, they will be provided separately.

Body weight results measured by subjects at home from virtual visits due to COVID-19 impact will not be included in the vital signs summary, but will be included in the listing with a flag to indicate which records were collected at home.

7.4. Concomitant Medications

Medications collected during the study will be coded using the current version of the World Health Organization (WHO) Drug dictionary.

Concomitant medications are defined as medications taken while a subject took study drug. Use of concomitant medications will be summarized by therapeutic subgroup (ATC level 2) and preferred name using the number and percentage of subjects for each treatment group. A subject reporting the same medication more than once will be counted only once when calculating the number and percentage of subjects who received that medication. The summary will be ordered in descending overall frequency, first by ATC class and then by preferred term. For drugs with the same frequency, sorting will be done alphabetically.

For the purposes of analysis, any medications with a start date prior to or on the first dosing date of study drug and continued to be taken after the first dosing date, or started after the first dosing date but prior to or on the last dosing date of study drug will be considered concomitant medications. Medications started and stopped on the same day as the first dosing date or the last dosing date of study drug will also be considered concomitant. Medications with a stop date prior to the date of first dosing date of study drug or a start date after the last dosing date of study drug will be excluded from the concomitant medication summary. If a partial stop date is entered, any medication with the month and year (if day is missing) or year (if day and month are missing) prior to the date of first study drug administration will be excluded from the concomitant medication summary. If a partial start date is entered, any medication with the month and year (if day is missing) or year (if day and month are missing) after the study drug stop date will be excluded from the concomitant medication summary. Medications with completely missing start and stop dates will be included in the concomitant medication summary, unless otherwise specified. Summaries will be based on the Safety Analysis Set. No formal statistical testing is planned.

All concomitant medications (other than per-protocol study drugs) will be provided in a by-subject listing sorted by subject ID number and administration date in chronological order.

7.5. Electrocardiogram Results

A frequency table of the investigators' assessment of ECG results at each visit will be presented by treatment group, using the following categories: normal; abnormal, not clinically significant; abnormal, clinically significant. The number and percentage of subjects in each classification group will be presented.

No formal statistical testing is planned.

A by-subject listing for ECG assessment results will be provided by subject ID number and time point in chronological order.

7.6. Other Safety Measures

A data listing will be provided for subjects who become pregnant during the study.

[REDACTED]

[REDACTED]

[REDACTED]

[REDACTED]

[REDACTED]

[REDACTED]

[REDACTED]

[REDACTED]

[REDACTED]

9. SOFTWARE

SAS[®] Software Version 9.4. SAS Institute Inc., Cary, NC, USA.

10. SAP REVISION

Revision Date (DD MMM YYYY)	Section	Summary of Revision	Reason for Revision
Original Gilead draft (11 February 2022)			
Draft 0.3 (11 July 2022)	Global	Editorial changes have been made throughout the SAP, where appropriate	To align with GLPG wording / template
	4.4	Added assessment of Ukrainian conflict impact	To better understand the Ukrainian conflict impact on subject disposition and missing data
	6.2	Added remission by CDAI and PRO2 as efficacy endpoints	To support the secondary endpoints.
	6.3, 7.1.8	Added subgroup analyses for efficacy endpoints and adverse events	To assess benefit/risk in subjects who completed the parent study and subjects who met protocol-specified efficacy discontinuation criteria
Draft 0.4 (1 Augustus 2022)	Global	Editorial changes have been made throughout the SAP, where appropriate	For clarification, based on team feedback
	5.2	Added baseline disease characteristics by subgroup	To complement the efficacy/safety subgroup analyses
	7.1.6	AEs will be presented ordered by total frequency, not alphabetically	Requested by medical writing
	7.5	Addition of ECG shift table	Requested by medical leads
	Global	Clarifications and corrections have been made throughout the SAP, where appropriate	Based on dry-run findings
Draft 0.5 (12 November 2022)	3.4	Update definition subgroups.	Based on internal discussion
	4.4.5	Replacing COVID impact indicator by listing of AEs related to COVID	The impact indicator is a Gilead-defined analysis. Not deemed valuable
	7.4	Addition of ATC level 2 in summaries of concomitant medications	Requested by medical leads
	7.5	ECG shift table replaced by frequency table	Baseline ECG not available in this study
	Title page	Update medical leader	

Final Version 1.0 (13 January 2023)	4.4	Reduction of planned analyses related to the impact of the Ukrainian conflict	Data availability
	5.2	Update prednisone dose categories	Requested by medical leads
	7.1.4	Added section on the handling of “action taken” information in the summaries of AEs	Clarification
	Appendix 5	Addition of MST lists based on the latest MedDRA version	For transparency on which lists were used at the time of analysis
Final Version 2.0 (1 August 2023)	3.2, 3.4, 5.1, 5.2, 6.3	Extension of analyses of baseline characteristics and efficacy endpoints in the subset of induction non-responders: by prior exposure, addition of imputation rules	For better understanding of this specific subgroup
	7.1.7	Removal of specific AE summaries	Considered unnecessary by the team
	7.1.8	Addition of subcategories VTE	Request medical safety
	7.1.9	Removal of subgroup analyses for AE	Considered unnecessary by the team
	7.2.2	Removal lab shift tables	Considered unnecessary by the team

Appendix 1. Schedule of Assessments

	Day 1 ^a	Week 2	Week 4	Every 4 Weeks from Day 1	Week 12 and then every 12 Weeks from Day 1 Clinic Visit	Every 24 Weeks from Day 1 Clinic Visit	Every 48 Weeks from Day 1 Clinic Visit	Early Termination (ET) Visit	Post-Treatment (PTx) ^b
Study Procedures		± 3 days	± 3 days	± 7 days	± 7 days	± 7 days	± 7 days		± 3 days
Written Informed Consent	X								
Review Inclusion/Exclusion Criteria	X								
Medical History	X								
Symptom-Directed Examination (as needed)	X	X	X		X			X	X
Perianal fistulae assessment (for subjects rolling over from GS-US-419-4016 only) ^c					X			X	X
Vital Signs ^d	X	X	X		X			X	X
Height	X								
Weight	X	X	X		X			X	X
Hematology	X	X	X		X			X	X
Chemistry	X	X	X		X			X	X
Lipid Profile (fasting) ^e						X			
Urinalysis	X					X			
Pregnancy Test ^f	X		X	X				X	X
HBV DNA monitoring (Japan) ^g	X		X	X					
HBV DNA monitoring (other regions) ^h	X				X				
TB Assessment ⁱ	X						X		

	Day 1 ^a	Week 2	Week 4	Every 4 Weeks from Day 1	Week 12 and then every 12 Weeks from Day 1 Clinic Visit	Every 24 Weeks from Day 1 Clinic Visit	Every 48 Weeks from Day 1 Clinic Visit	Early Termination (ET) Visit	Post-Treatment (PTx) ^b
Study Procedures		± 3 days	± 3 days	± 7 days	± 7 days	± 7 days	± 7 days		± 3 days
12-lead ECG							X		
Serum immunoglobulin	X					■			
e-Diary Instruction & Review ¹	X	X	X		X				
PRO2 ^m	X	X	X		X			X	
CDAI ^m	X	X	X		X			X	
Enrollment	X								
Study Drug Dispensation	X		X		X				
Adverse Events ^o	X	X	X		X			X	X
Concomitant Medications	X	X	X		X			X	X

a Day 1 visit for this study may occur at the same time as the final scheduled treatment visit of the prior filgotinib study. All procedures necessary for the final visit in the prior filgotinib study will be completed as well as any additional procedures required for this study. Procedures that are duplicates of the final visit from prior filgotinib study do

- not need to be performed again for this protocol. Day 1 may be delayed up to 10 days. If Day 1 of LTE is not the same as the last study visit of the prior study, a full set of Day 1 procedures should be performed. If a subject has already taken study drug for that day within the parent protocol, first dose should take place on Day 2.
- b The Post-Treatment (PTx) Visit should occur 30 days after the last dose of study drug.
 - c The perianal fistula assessment entails tracking the clinical status of draining external openings of perianal fistulae that were identified at baseline of Study GS-US-419-4016 . For additional details on the perianal assessment, refer to the Perianal Fistula Assessment Manual
 - d Vital signs include resting blood pressure, respiratory rate, pulse, and temperature.
 - e Fasting means no food or drink except water, for 8 hours
 - f Females who are of childbearing potential only. A urine pregnancy test must be completed in clinic every 4 weeks at a minimum. If any pregnancy test is positive, study drug should be immediately interrupted and the subject should have a serum pregnancy test in clinic.
 - g In Japan, subjects with negative HBsAg, positive HBcAb and/or positive HBsAb in a parent CD protocol require HBV DNA monitoring every 4 weeks in accordance with local guidelines (Protocol Section 6.2.1).
 - h In other regions, subjects with negative HBsAg and positive HBcAb require HBV DNA monitoring every 3 months in accordance with local guidelines (Protocol Section 6.2.1)
 - i Subjects who were previously treated for TB do not need to have yearly QuantiFERON® (or centrally reported equivalent assay) tests but should be screened at least yearly for signs and symptoms of reactivation.
 - j [REDACTED]
 - k [REDACTED]
 - l At Day 1 visit, review diary of subject reported components from parent study. Subjects should begin filling out the Diary on Day 1 visit and continue to fill it out throughout the study.
 - m Colonoscopy with biopsies is optional per standard of care. The date of the procedure may be requested for accuracy of data analysis.
 - n [REDACTED]
 - o Ongoing AEs from previous filgotinib studies should be recorded as medical history. Collection of AEs and SAEs related to protocol-mandated procedures will begin once informed consent is signed and will continue through the Post-Treatment (PTx) Visit.

Appendix 2. CDAI and PRO2 Calculation

The total CDAI score is a weighted sum of all 8 variables as specified in [Table 11-1](#), and the PRO2 scores will be assessed according to [Table 11-2](#). Details for the calculations of CDAI and PRO2 scores at baseline and post-baseline visits are provided in this appendix.

Table 11-1. Calculation of Total CDAI Score

Variable no.	Variable	Variable description	Multiplier
1	Liquid or very soft stool	Daily stool count is summed for 7 days	2
2	Abdominal pain	Sum of 7 days of daily ratings as 0 = none, 1 = mild, 2 = moderate, 3 = severe	5
3	General wellbeing	Sum of 7 days of daily ratings as 0 = generally well, 1 = slightly below par, 2 = poor, 3 = very poor, 4 = terrible	7
4	Complications	Number of listed complications: - Arthritis or arthralgia - Erythema nodosum, pyoderma gangrenosum or aphthous stomatitis - Iritis or uveitis - Anal fissures or fistulae or abscess - Other fistula - Fever over 37.8 C [100 F] during past week	20 each
5	Use of anti-diarrheal medications	Use of diphenoxylate or loperamide or other opiate for diarrhea 0 = No, 1 = Yes	30
6	Abdominal mass	0 = none, 2 = questionable, 5 = definite	10
7	Hematocrit*	Males: 47 – Hct [%] Females: 42 – Hct [%] *Result must be greater than or equal to 0. If negative result enter 0	6 × difference
8	Weight*	Percentage deviation from standard weight (1 – weight / standard weight) × 100 *Limit of -10 (Result must be greater than or equal to -10)	1
CDAI score			TOTAL

CDAI = Crohn's Disease Activity Index; Hct = hematocrit

Table 11-2. Calculation of PRO2 Components

Variable no.	Variable	Variable Description
1	Liquid or very soft stool	Mean of the daily (liquid or very soft) stool count for 7 days
2	Abdominal pain	Mean of 7 days of daily ratings as 0 = none, 1 = mild, 2 = moderate, 3 = severe

Each PRO2 subscore will be rounded to the nearest integer (eg, 2) in the determination of subject eligibility for the study and calculation of endpoints.

The 3 patient-reported outcome components for CDAI (and each subscore for PRO2) are determined using an electronic daily diary, which collects subject reported components directly. Given that the ileocolonoscopy procedure (non-protocol-directed procedures) may impact the validity of the diary data, diary data collected 1 day prior to and on the day of the procedure will not be used in the calculation of CDAI and PRO2 subscores for all visits. Those days are called non-evaluable days.

Calculation of CDAI and PRO2 Scores for Baseline and Post-baseline Visits

The calculations of CDAI and PRO2 scores for baseline and post-baseline visits are specified below:

- 1) The Day 1 visit date will be used as the anchor day for baseline and following visit dates will be used as the anchor day for post-baseline visits. The visit date for each analysis visit will be selected as the anchor day among all scheduled visits and unscheduled visits where CDAI were assessed within the analysis window as defined in Section 3.8.2. Only diary data collected on evaluable days within a 10-day window which starts 10 days prior to the selected visit date (V-Day 1) and ends on the day prior to V-Day 1 will be used for calculation.
- 2) If there are 7 or more evaluable records within the 10-day window, take the **sum** of the 7 evaluable records closest to V-Day 1 for the corresponding CDAI subject-reported component. For the corresponding PRO2 component, take the **average** of the 7 evaluable records within the 10-day window closest to V-Day 1.
 - a) If there are 4 or more (but less than 7) evaluable records within this 10-day window, the average of the available records will be taken, and then multiplied by 7 for the corresponding CDAI patient-reported component. For the corresponding PRO2 component, the average of the available records will be taken.
 - b) If subjects do not have at least 4 evaluable records within this 10-day window, the corresponding CDAI patient-reported component, and the corresponding PRO2 component will not be calculated and will be considered as missing for that visit.

A schema of this approach and some examples are included below for further explanation:

Figure 1. Selection of Diary Data for the Calculation for Baseline and Postbaseline Visits

[figure not shown]

Table 11-3. Calculation of CDAI Patient-Reported Outcome Components and PRO2 Scores for Baseline and Post-baseline Visits

Example	Diary Day Looking Backwards from Visit Date (V-Day)										Days for Calculation	Sum of 7 Days (CDAI Patient-Reported Component)	Average of 7 Days (PRO2)
	-10	-9	-8	-7	-6	-5	-4	-3	-2	-1			
Diary Subscore 1	1	2	2	M	0	1	2	2	1	X	-2,-3,-4,-5,-6,-8,-9	10.0	1.4
Diary Subscore 2	M	M	1	M	X	IL	2	2	1	M	-2,-3,-4,-8	10.5	1.5
Diary Subscore 3	M	M	1	X	IL	M	M	2	1	M	-2,-3,-8	Missing	Missing
Diary Subscore 4	0	M	2	2	1	0	M	2	X	IL	-3,-5,-6,-7,-8,-10	8.2	1.2

M = Missing; IL = Ileocolonoscopy day; X = non-evaluable (due to preparation for ileocolonoscopy).

Days are named relative to visit date (V-Day 1), where V-Day – 1 is the day prior to V-Day 1.

Rounding of subscores into one decimal place is for displaying purpose only. When calculating the total CDAI scores, the subscores will not be rounded.

- The CDAI total score for a specific visit is based on a weighted sum (rounded to the nearest integer) of all 8 components. The CDAI total score will be set to 0 in the case the calculation leads to a CDAI total score < 0. Each component will be selected within the analysis window as defined in Table 3-1 in Section 3.8.2.

If subjects have at least 1 of the 8 CDAI components missing, then their total CDAI score will be considered missing. If at least 1 out of the 6 complications under the complication component is missing, then the complication component will be considered missing.

- 4) The PRO2 subscores for a specific visit are based on the evaluation of liquid or very soft stool frequency and abdominal pain subscores individually (rounded to the nearest integer) within the analysis window as defined in Section 3.8.2.

Source of Information Used for CDAI and PRO2 Calculation

The sources of information used for the calculations of CDAI and PRO2 scores as described above are given in **Error! Reference source not found.** (the calculated scores from ERT data will not be used for data analysis). Hematocrit results collected from local laboratories and body weight measured at home due to COVID-19 impact will be used in CDAI calculation.

Table 11-4. Sources of Information for Calculating CDAI and PRO2 Scores

Variable in Calculation	Data Source
Visit Date	VISITDAT in VISDT dataset from eCRF data
Stool Frequency Diary Data	QSSTRESN in DIARY dataset with QSTESTCD="SOFSTOOL" from vendor ERT data
Abdominal Pain Diary Data	QSSTRESN in DIARY dataset with QSTESTCD="ABDPAIN" from vendor ERT data
Subject Standard Weight	SEX_STD in DM dataset and HEIGHT_STD in VSPERF dataset from eCRF data will be used to determine the standard weight based on Appendix 4 .
Subject Actual Weight	WEIGHT_STD in VSPERF dataset from eCRF data
Hematocrit Value	CNVRESN in COVLAB dataset with LBTEST="Hematocrit" from vendor Covance data or LBORRES in LB_HEM dataset with LBTEST="Hematocrit" from eCRF data if collected in local laboratory due to COVID-19 impact

Note: eCRF = electronic case report form(s). ERT is the vendor that electronically collects patient and investigator reported outcomes.

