## **6.5. Post-Treatment Assessments ( $\pm$ 3 days)**

All subjects must complete the Post-Treatment (PTx) assessments 30 days after the last dose of study drug.

The following evaluations are to be completed:

- Symptom-directed PE
- Complete perianal fistulae assessment (for subjects rolling over from GS-US-419-4016 **only**)
- Obtain weight
- Review AEs and concomitant medications
- Obtain vital signs (resting blood pressure, respiratory rate, pulse and temperature)
- Obtain blood samples (reference Study Procedures Table [[Appendix 2](#)])
- Obtain urine sample (reference Study Procedures Table [[Appendix 2](#)])

— Sample will be used for pregnancy test (for females of childbearing potential only)

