1.3. Sample Size and Power

No formal hypothesis testing is planned for this study and sample size calculation is not conducted. All subjects who have completed or met protocol-specified efficacy discontinuation criteria in a parent study (GS-US-419-4015, GS-US-419-4016, or GS-US-419-3895) may enroll in this study. The projected number of subjects enrolled is approximately 1000.

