3.8.2. Analysis Visit Windows

Subject visits might not occur on protocol-specified days. Therefore, for the purpose of analysis, observations will be assigned to analysis windows.

The analysis windows for CDAI, PRO2, vital signs, weight, hematology, and chemistry are provided in Table 3-1. The analysis windows for lipid profile, serum immunoglobulin, [REDACTED] [REDACTED] are provided in Table 3-2. The analysis windows for [REDACTED]

Table 3-1. Analysis Visit Windows for CDAI, PRO2, Vital Signs, Weight, Hematology and Chemistry

Nominal Visit	Nominal Study Day	Visit Window Study Day	
		Lower Limit	Upper Limit
Baseline	1	(none)	1
Week 2	15	2	22
Week 4	29	23	57
Week 12	85	58	127
Week 24	169	128	211
Week 36	253	212	295
Week 48	337	296	379
Week 60	421	380	463
Week 72	505	464	547
Week 84	589	548	631
Week 96	673	632	715
Week 108	757	716	799
Week 120	841	800	883

Nominal Visit	Nominal Study Day	Visit Window Study Day	
		Lower Limit	Upper Limit
Week 132	925	884	967
Week 144	1009	968	1051
Week 156	1093	1052	1135
Week 168	1177	1136	1219
Week 180	1261	1220	1303
Week 192	1345	1304	1387
Week 204	1429	1388	1471
Week 216	1513	1472	1555
Week 228	1597	1556	1639
Week 240	1681	1640	1723
Week 252	1765	1724	1807
Week 264	1849	1808	1891
Week 276	1933	1892	1975
Week 288	2017	1976	2059
Week 300	2101	2060	2143
Week 312	2185	2144	2227
Week 324	2269	2228	2311
Week 336	2353	2312	2395
Week 348	2437	2396	2479
Week 360	2521	2480	2563
Week 372	2605	2564	2647
Week 384	2689	2648	2731
Week 396	2773	2732	2815
Week 408	2857	2816	2899
Week 420	2941	2900	2983
Week 432	3025	2984	≥ 3025

CDAI = Crohn's Disease Activity Index; PRO2 = patient reported outcome consisting of 2 items: abdominal pain severity and liquid stool frequency

Table 3-2. Analysis Visit Windows for Lipid Profile, Serum Immunoglobulin,

Nominal Visit	Nominal Study Day	Visit Window Study Day	
		Lower Limit	Upper Limit
Baseline	1	(none)	1
Week 24	169	2	253
Week 48	337	254	421
Week 72	505	422	589
Week 96	673	590	757
Week 120	841	758	925
Week 144	1009	926	1093
Week 168	1177	1094	1261
Week 192	1345	1262	1429
Week 216	1513	1430	1597
Week 240	1681	1598	1765
Week 264	1849	1766	1933
Week 288	2017	1934	2101
Week 312	2185	2102	2269
Week 336	2353	2270	2437
Week 360	2521	2438	2605
Week 384	2689	2606	2773
Week 408	2857	2774	2941
Week 432	3025	2942	≥ 3025

3.8.3. Selection of Data in the Event of Multiple Records in an Analysis Visit Window

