Depending on the statistical analysis method, single values may be required for each analysis window. For example, change from baseline by visit usually requires a single value, whereas a time-to-event analysis would not require 1 value per analysis window.

If multiple valid, nonmissing measurements exist in a postbaseline analysis window, records will be chosen based on the following rules if a single value is needed:

- The record closest to the nominal day for that visit will be selected.
- If there are 2 records that are equidistant from the nominal day, the later record will be selected.
- If there is more than 1 record on the selected day, the average will be taken for continuous data and the worse severity will be taken for categorical data, unless otherwise specified.

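### As written, SAP Appendix 2 can combine diary data from before early termination with post-treatment hematocrit and weight in a stopping subject's last CDAI score

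*SAP*

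**What the plan says.** SAP Appendix 2, step 1, gives the diary components a date. The visit for each analysis visit is "selected as the anchor day among all scheduled visits and unscheduled visits where CDAI were assessed within the analysis window", and only evaluable diary entries from the 10 days before that visit count. The step that forms the total score has a wider scope: "Each component will be selected within the analysis window as defined in Table 3-1 in Section 3.8.2".

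Hematology and weight share those windows: "The analysis windows for CDAI, PRO2, vital signs, weight, hematology, and chemistry are provided in Table 3-1" (SAP 3.8.2). From Week 24 to Week 420 each window is 84 days wide. Where a window holds several records, SAP 3.8.3 sets the general rule, "The record closest to the nominal day for that visit will be selected", and a tie goes to the later record. Table 11-4 names the datasets for hematocrit and weight but no visit.

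The ET visit collects CDAI, PRO2, hematology and weight (Protocol 6.6 and the Study Procedures Table in Protocol Appendix 2). The PTx visit collects hematology and weight but neither CDAI nor PRO2. On its timing: "All subjects must complete the Post-Treatment (PTx) assessments 30 days after the last dose of study drug" (Protocol 6.5, ±3 days).

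**The concern.** A PTx visit can never be the diary anchor, because CDAI is not assessed there. It can still place a hematocrit and a weight in the same analysis window as the ET visit. If PTx lies nearer the nominal day, the component rule picks its values, and the score mixes two dates and two treatment states. Such a composite is not the CDAI of any day.

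Nothing elsewhere prevents this. Appendix 2 says the vendor's calculated scores will not be used for analysis. The boundary of last dose plus 30 days in SAP 7.2 governs laboratory summaries and would itself admit a PTx sample taken at 30 days. SAP 3.8, SAP Section 6 and Appendix 2 contain no exclusion of PTx records from CDAI.

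Change in CDAI is a secondary endpoint (SAP 6.2.1), and a score below 150 defines CDAI remission (SAP 6.1.1). The score at risk is the last one a stopping subject contributes. In the induction non-responder subgroup, SAP 6.3 carries the latest value forward after premature discontinuation other than study closure, so one mixed score can recur at later visits.

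**Working it through.** **Inputs.** Windows: SAP Table 3-1. Selection rule: SAP 3.8.3. PTx timing: Protocol 6.5. CDAI weights: SAP Table 11-1. Assumption for the main count: ET on the day of last dose, PTx 30 days later.

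**1. Reproduce the windows.** The nominal day is 7 × week + 1, and limits are midpoints between nominal days.
- Nominal days: Week 4 = 29, Week 12 = 85, Week 24 = 169, Week 36 = 253.
- Week 24: (85 + 169)/2 = 127, so the lower limit is 128; (169 + 253)/2 = 211. Width 211 − 128 + 1 = 84 days.
- Week 12: (29 + 85)/2 = 57, so the lower limit is 58; the upper limit is 127. Width 70 days.

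These match Table 3-1.

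**2. One subject.** ET is on Day 150 and PTx on Day 180; both lie in the Week 24 window.
- Diary: Day 150 is the only CDAI visit, so the diary window is Days 140 to 149.
- Hematocrit and weight: Day 150 is 169 − 150 = 19 days from nominal, and Day 180 is 180 − 169 = 11 days. SAP 3.8.3 selects Day 180.

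**3. Count the ET days.** For ET on day d and a gap of g days to PTx, the PTx values are chosen when d + g is inside the window and |d + g − nominal| ≤ |d − nominal|. The second condition reduces to d ≤ nominal − g/2. With g = 30, ET must be at least 15 days before the nominal day.

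| Window | Condition | ET days affected | Share of ET days |
|---|---|---|---|
| Week 2 (2–22) | PTx falls outside the window | none | 0 of 21 |
| Week 4 (23–57) | d ≤ 14, below the window | none | 0 of 35 |
| Week 12 (58–127) | d ≤ 70 | 58–70 | 13 of 70 (19%) |
| Week 24 (128–211) | d ≤ 154 | 128–154 | 27 of 84 (32%) |

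Each later 84-day window repeats the Week 24 result. The affected ET days precede the scheduled visit (Week 24: Day 162 at the earliest, from 169 − 7), so ET is normally the only CDAI visit in the window.

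**4. Vary the gap.** If ET falls 0 to 14 days after last dose (assumed) and PTx 27 to 33 days after it, g runs from 13 to 33. The share is then 25 to 35 of 84 days (30% to 42%) for Week 24 and later, and 11 to 21 of 70 (16% to 30%) for Week 12. Week 4 stays at none. Week 2 is touched only at the shorter gaps (1 of 21 days at g = 20, 7 of 21 at g = 13).

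**5. ET near the scheduled day.** If ET is within 7 days of nominal and PTx is 27 to 33 days later, PTx is at least 27 − 7 = 20 days from nominal against at most 7 for ET. No mixed score arises.

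**6. Points per score.** One percentage point of hematocrit moves CDAI by 6, except where the component is floored at 0 (hematocrit above 47% in men or 42% in women). Weight adds 1 point per 1% of standard weight. The documents give no expected hematocrit shift; an assumed shift of 1 to 4 points would move CDAI by 6 to 24.

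**The case against.** The mixing is inferred from two rules read together. Appendix 2 speaks of the total score for a specific visit, so the window could be read only as an outer limit on that visit's records. Appendix 2 also cites SAP 3.8.2, not 3.8.3, whereas SAP 7.2.1 and 7.3 cite 3.8.3 by number. Same-visit data may be what is intended. This objection stands in part. But the sentence names the window and not the visit, 3.8.3 sits among the general conventions, and without it no rule chooses between two hematocrit values in one window. Two programmers could reach different scores.

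It is also fair that the study is descriptive: "No formal hypothesis testing is planned for this study and sample size calculation is not conducted" (SAP 1.3). Only a stopping subject's last CDAI window is exposed, and any clustering of ET at scheduled visits lowers the share. Placebo subjects at unblinding, for example, attend at their next scheduled visit or earlier (Protocol 6.7). These points limit the importance of the problem but do not remove it.

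A reader might infer more than the documents support:
- That hematocrit may come from anywhere in the window. SAP 3.8.3 narrows it to the record nearest the nominal day; in the affected cases that rule is what selects PTx.
- That about a third of stoppers get a mixed score. The 32% counts ET days; it would apply to subjects only if ET days were spread evenly, and no distribution is given.
- That the affected subjects mostly stopped for worsening. The mix of discontinuation reasons is not given.
- That the laboratory retests in Protocol 3.5.2 cause the same problem. They fall within 3 to 7 days (creatinine 7 to 14) and do not produce a 30-day off-drug gap.

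**Conclusion.** The point holds. Followed as written, with SAP 3.8.3 as the selection rule, Appendix 2 produces CDAI scores whose diary part precedes ET and whose hematocrit and weight come from PTx, up to about 30 days later and off drug. A later ET shortens that gap. The counts of 27 of 84 and 13 of 70 ET days rest on ET at last dose and PTx at +30 days.

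Bias in group means is not shown and cannot be computed: the number of affected subjects and the size and direction of any hematocrit shift are not in the documents. The exposure is the last CDAI window of subjects who stop, plus carry-forward in the induction non-responder subgroup. PRO2 uses diary data only, and the primary safety endpoint is not reached by this route. The change is worth making because the rule affects a secondary endpoint and correcting it costs little.

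**What to change.** In SAP Appendix 2, replace the component-selection sentence with a rule of this content:
- For post-baseline visits, hematocrit and weight are taken from the anchor visit chosen in step 1: the record on the anchor date or, if there is none, the nearest record within a short stated interval (for example 7 days).
- PTx records are not used for CDAI.
- Baseline components remain restricted to records on or before the first dosing date, as SAP 3.8.4 requires. Without this line, an interval running both ways could let a post-dose value into baseline.

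Do not add a limit counted from the last dose. ET can fall some time after dosing stops, and such a limit could discard a valid anchor-date hematocrit and make the whole score missing.

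With this rule the number of ET days giving a mixed score by this route falls to 0 in every window. The cost is a short SAP edit and a change to the derivation program, documented in the CSR as SAP Section 1 requires for changes after finalization. A few CDAI scores will become missing where no hematocrit or weight lies close to the anchor visit.
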